6.3.2.2. ECG Evaluations

The ECG parameters reported for this study per Protocol C5041011 (APD334-210) amendment 2.0 will be summarized by visits.

ECG Markedly Abnormal Criteria

Markedly abnormal quantitative ECG measurements will be identified in accordance with the following predefined markedly abnormal criteria:

- Absolute values in QT and QTcF:
 - ≥ 450 ms (male) or ≥ 470 ms (female) in QTcF
 - > 500 ms in QT
- Change from Baseline in QT and QTcF:
 - > 30 ms increase from Baseline

- > 60 ms increase from Baseline

ECG Evaluations

The following summaries will be provided for ECG data:

- Value and change from Baseline by visit (for quantitative measurements).
- Incidence of markedly abnormal values (defined in "ECG Markedly Abnormal Criteria" above) and AV blocks by visit.

Listings of ECG results, including first dose cardiac monitoring, and discharge criteria for first dose cardiac monitoring will be provided.

A listing of all ECG assessments over time in participants meeting markedly abnormal criteria will also be provided. In this listing,

- For each participant, only ECG parameters ever meeting markedly abnormal criteria will be included.
- For each participant, if there is at least one assessment meeting markedly abnormal criteria for a given ECG parameter, then all assessments collected of this ECG parameters over time will be included.

6.3.2.3. Cardiac Holter Monitoring

hHR

Value and change from baseline in hHR will be descriptively summarized by hourly timepoint.

Time to first nadir hHR post-dose will be descriptively summarized as a continuous outcome measure in the Modified Safety Set. The number and percentage of participants who reached their first nadir hHR at each nominal hourly timepoint (eg, hour 1, hour 2, etc.) will also be descriptively summarized.

Cardiac Abnormal Findings

Incidence of participants with abnormal findings flagged by cardiac central laboratory will be descriptively summarized.

Incidence of participants with low heart rate as defined in Section 3.3.2.1 will be descriptively summarized.

Data Listings

Holter recording data on Day 1 will be listed.

6.3.2.4. Vital Sign

The vital sign parameters reported for this study per Protocol C5041011 (APD334-210) amendment 2.0 will be summarized by visits. Table 8 below lists the markedly abnormal criteria for vital signs.

Table 8. Markedly Abnormal Criteria for Vital Signs

Vital Sign Parameter	Unit	Low	High
SBP	mm Hg	≤ 90 mm	> 150 mm Hg
DBP	mm Hg	≤ 50 mm	> 90 mm Hg
Heart rate	bpm	< 40 bpm	> 100 bpm
		< 50 bpm	_
		< 50 bpm and decrease from	
		predose (Baseline) of > 10	
		bpm at 4 hours on Day 1 or	!
		Day 2 or remonitoring visit	

bpm: beats per minute; DBP: diastolic blood pressure; SBP: systolic blood pressure

The following summaries will be provided for vital signs data:

- Value and change from Baseline by visit.
- Value and change from predose on Day 1 (as reported on the eCRF) by timepoint.
 - For heart rate only, value and change from predose to minimum postdose heart rate on Day 1 will be included in the same table.
- Incidence of markedly abnormal values (defined in Table 8 above).
- Listing of participants meeting markedly abnormal criteria.
- Incidence of minimum heart rate on Day 1 by postdose timepoint (1, 2, 3, 4, and > 4 hours postdose, and Day 1 overall) and heart rate interval (≥65, 60 to 64, 55 to 59, 50 to 54, 45 to 49, 40 to 44, < 40 bpm).
 - If minimum heart rate is attained at multiple postdose timepoints, only the earliest timepoint will be counted in this incidence summary.
- Time to minimum heart rate on Day 1 by planned hourly timepoint (if minimum heart rate is attained at multiple postdose timepoints, only the earliest timepoint will be counted).
 - Actual time elapsed from first dose to minimum heart rate on Day 1 will also be summarized using descriptive statistics (n, mean, SD, median, minimum, and maximum) in the same table.

For participants with extended monitoring or remonitoring, a listing of systolic blood pressure, diastolic blood pressure, heart rate values, and change from predose in all parameters on Day 1, Day 2, and any remonitoring visit will be provided.

Vital signs derivation for temperature: temperature ($^{\circ}$ C) = (5/9) (temperature ($^{\circ}$ F) – 32).

6.3.2.5. Pulmonary function tests

PFT Markedly Abnormal and Potentially Important Criteria

Markedly abnormal quantitative PFT measurements will be identified in accordance with the following predefined markedly abnormal criteria:

- % Predicted FEV1 < 50%
- % Predicted FVC < 50%
- % Predicted FEV1/FVC ratio < 50%

Potentially important PFT measurements will also be identified using the criteria below:

- Percent decrease from Baseline > 20% in FEV1, ie, percent change from Baseline < -20%
- Percent decrease from Baseline > 20% in FVC, ie, percent change from Baseline < 20%
- Percent decrease from Baseline >20% in DLCO (if available), ie, percent change from Baseline < -20%
- Percent decrease from Baseline ≥30% in FEV1, ie, percent change from Baseline ≤ -30%
- Percent decrease from Baseline ≥30% in FVC, ie, percent change from Baseline ≤ -30%
- Percent decrease from Baseline ≥30% in DLCO (if available), ie, percent change from Baseline < -30%

The PFT parameters reported for this study per Protocol C5041011 (APD334-210) amendment 2.0 will be summarized by visits.

The following summaries will be provided for PFT data descriptively:

- Value and change from Baseline by visit.
- Incidence of markedly abnormal and/or potentially important PFT values by visit per "PFT Markedly Abnormal and Potentially Important Criteria" above.

All PFT data will be listed. Abnormal PFTs, markedly abnormal and/or potentially important PFT values will be flagged in the listing.

6.3.2.6. Ophthalmoscopy and Optical coherence tomography

The following summaries will be provided for ophthalmoscopy and optical coherence tomography (OCT) data:

- Values and change from Baseline in central foveal thickness and intraocular pressure by visit.
- Incidence of markedly abnormal change in central foveal thickness (CFT) (> 40 μ m increase from Baseline in CFT in either eye) by Visit.
- Categorical result in ophthalmoscopy with OCT parameters by visit (the categories are listed on the eCRF).

A listing of all ophthalmoscopy and OCT assessments will be provided. A listing of participants who ever reported an abnormality in OCT will also be provided. Additionally, a listing of retinal photograph and eye pressure assessments will be provided for participants who experienced an AE related to eye disorders.

6.3.2.7. Tuberculosis Questionnaire

Tuberculosis Questionnaire at screening and post screening will be listed.

6.4. Subset Analyses

The following major subgroup analyses for the primary and key secondary efficacy endpoints will be performed based on PAS, in order to explore whether the treatment effects are consistent across different subgroups.

- Age (years):
 - \rightarrow or \leq median value (based on PAS)
 - \geq or < 65 years
- Sex (Male, Female)
- Race (White or Non-White)
- Race (White, Black or African American, Asian, Other, where Other captures the remaining races)
- Ethnicity (Hispanic or Latino, Not Hispanic or Latino)
- Region (North America, Western Europe, Eastern Europe, Other)
- Baseline oral corticosteroid usage (yes or no) *
- Naïve to biologic or JAK inhibitor therapy at study entry (yes or no) *
- Baseline fecal calprotectin > or \le median value (based on PAS)
- Baseline CRP > or \leq median value (based on FAS)
- Prior Oral 5-ASA Failure Only (yes or no)

• Naïve to biologic or JAK inhibitor therapy who failed corticosteroid and/or thiopurines (yes or no)

The main subgroup analyses for primary and key secondary efficacy endpoints will be based on the same MH weighted method as mentioned in Section 5.2.1 except that

- For subgroup baseline oral corticosteroid usage (yes or no), the reported stratum of baseline oral corticosteroid usage (yes or no) will not be used in MH weighted method.
- For subgroup naïve to biologic or JAK inhibitor therapy at study entry (yes or no), the
 reported stratum of naïve to biologic or JAK inhibitor therapy at study entry (yes or
 no) will not be used in MH weighted method.

Additional subgroups may be assessed, if deemed necessary. If any subgroup includes < 5% of all participants, no inferential statistics will be generated.

Graphical display (eg, forest plots) of the treatment differences between treatment groups will be presented for each of the primary and key secondary efficacy endpoints. The treatment differences between treatment groups, along with 95% CIs, that are obtained from MH weighted method mentioned above will be displayed.

6.5. Baseline and Other Summaries and Analyses

6.5.1. Baseline Summaries

Demographics and medical history including variables defined in Section 3.5 will be summarized by treatment group.

6.5.2. Study Conduct and Participant Disposition

Among the randomized participants, the number and percent of participants who completed/discontinued study treatment, reasons off treatment, the number and percent of participants who completed/discontinued the study, and reasons off study will be summarized. This summary will also be provided by region and country. The number and percent of participants in each analysis set will be summarized for all randomized participants. An additional summary of the number of participants screened, the number of screen-failed participants, and reason for screen failure will be presented for all screened participants. If there are participants whose blind was broken during the study, a listing of these participants will be provided. The number of participants whose visit was impacted by the COVID-19 pandemic will also be summarized.

According to ICH E3 and ICH E3(R1), important protocol deviations are a subset of protocol deviations that might significantly affect the completeness, accuracy, and/or reliability of the study data or that might significantly affect a participant's rights, safety, or well-being (ICH 1996, ICH 1998). All-important protocol deviations will be identified before study unblinding. The identified important protocol deviations will be summarized by protocol

^{*}actual stratum (based on medications reported on the eCRF)

deviation categories (Section 9.1.6). All protocol deviations will be listed, including whether a protocol deviation that occurred during by the COVID-19 pandemic was impacted by the COVID-19 pandemic (Yes or No) or the war between Russia and Ukraine (Yes or No).

6.5.3. Study Treatment Exposure

6.5.3.1. Duration of Study Treatment Exposure

The date of first and last study treatment administration will be taken from the Day 1 Onsite Dosing Administration eCRF and the End of Study eCRF, respectively. Interruptions, compliance, and dose changes are not taken into account for duration of exposure. Exposure to study treatment in weeks will be summarized for the Safety Set.

Duration of exposure (weeks) = (date of last study treatment administration – date of first study treatment administration + 1) / 7. For participants with missing Date of Last Dose on the End of Study eCRF, their date of last study treatment administration will be imputed by the last date of all dosing administration start/stop dates recorded.

6.5.3.2. Dose interruption and Overdose

For dose interruptions, the frequency and percentage will be provided for the following:

- participants who had at least 1 dose interruption
- participants who had at least 1 dose interruption of > 7 days
- participants who had at least 1 dose interruption of > 14 days

For overdose, the frequency and percentage will be provided for the following:

- participants who had 1 overdose
- participants who had > 1 overdose will be summarized.

6.5.3.3. Study Treatment Compliance

For study treatment compliance, the total number of tablets expected, total number of tablets taken, total number of tablets missed, overall compliance with study treatment, and frequency and percentage of participants with overall compliance of < 80% or > 120% will be summarized for the Safety Set for the entire study.

Compliance to study treatment is based on the Drug Accountability eCRF and will be calculated as the total number of tablets taken (total dispensed – total returned) divided by the number of tablets expected during the Treatment Period, expressed as a percentage, refer to calculations below.

The total number of tablets expected is defined as the number of tablets that a participant is expected to have taken between their first and last study treatment administration and is numerically identical to the participant's overall study treatment exposure, since the

medication is to be taken once daily. On any site visit day, the medication is to be held and taken at the site, after all predose assessments have been completed.

• Overall compliance to study treatment will be calculated as follows; total number of tablets returned subtracted from total number of tablets dispensed, divided by the duration of treatment, multiplied by 100.

For all bottles not returned, it will be assumed that all dispensed tablets were taken. For each participant, if a high percentage (> 25%) of bottles were not returned by a participant, additional analyses may be done where bottles not returned are excluded from the overall compliance calculation for the participant. In such analysis, the date of last dose or the date of last bottle return, whichever is earlier, will be used as the "date of last dose" in the calculation above.

Both scheduled and unscheduled study treatment dispensations will be used in the compliance calculation. Overall compliance calculations will be performed for the entire study and will be used in determining inclusion/exclusion of participants in the respective Per Protocol Set.

6.5.4. Concomitant Medications and Nondrug Treatments

Medications will be captured on the Concomitant Medications eCRF and coded using the WHO Drug dictionary (GlobalB3_March 2024). Refer to Section 9.1.5 for handling of partial dates for medications. In the case where it is not possible to define a medication as prior or concomitant, the medication will be classified by the worst case (ie, concomitant)

- 'Prior' medications are medications which started and stopped prior to the first dose of study treatment.
- 'Concomitant' medications are medications which started prior to, on or after the first dose of study treatment AND ended on or after the date of first dose of study treatment or were ongoing at the end of the study.

Concomitant medications will be summarized by Anatomical Therapeutic Chemical (ATC) Level 2 and Preferred Drug name for the Safety Set. Concomitant medications used for UC will be flagged as such on the Concomitant Medications eCRF and summarized by ATC Level 2 and Preferred Drug name for the Safety Set.

7. INTERIM ANALYSES

There are no interim analyses planned for this study.

9. APPENDIX

9.1. Data Derivation Details

9.1.1. Demographics and Baseline Characteristics Related variables

- Duration of UC (year) = (Informed consent date Date of diagnosis + 1) / 365.25
- Weight (kg) = Weight (lb) \times 0.4536
- Height (cm) = Height (in) \times 2.54
- Height (m) = Height (in) \times 0.0254 = Height (cm) \times 0.01
- BMI (kg/m^2) = Weight (kg) / Height $(m)^2$

9.1.2. Reference Start Date and Study Day

Study Day will be calculated from the reference start date and will be used to show start/stop day of assessments and events. Reference start date is defined as the date of first dose (Day 1) and will appear in every listing where an assessment date or event date appears.

• If the date of the event is on or after the reference start date, then:

Study Day = (date of event - reference start date) + 1

• If the date of the event is prior to the reference start date, then:

Study Day = (date of event - reference start date)

In the situation where the event date is partial or missing, Study Day and any corresponding durations will appear missing in the listings.

9.1.3. Retests, Unscheduled Visits, and Early Termination Data

For by-visit analyses and summaries, efficacy, safety, HRQoL, and biomarker data (including scheduled, retests, unscheduled, and early termination) will be assigned to visits after the application of the windowing conventions described in Section 9.1.4 below. All measurements will be considered in summaries of abnormalities or worst-case values post-Baseline. The visit windowing will be applied before missing data are imputed. Listings will include scheduled, unscheduled, retest, and early termination data.

9.1.4. Definition and Use of Visit Windows in Reporting

All scheduled study visits are defined relative to Study Day 1, the date of first dose. Scheduled visit windows are defined in Clinical Study Protocol APD334-210 Amendment 2.0 Appendix 1: SCHEDULE OF ASSESSMENTS. A windowing convention will be used to determine the analysis visit value for a given measurement and will be applicable for all byvisit summaries and analyses for efficacy and safety data. Refer to Table 9 below for specific visit windows.

Table 9. Analysis Visit Windows for Efficacy and Safety Analyses

For all efficacy (except endoscopy/MI	MS/histology), efficacy-related biomarkers, safety labs and vital
signs	vis/instology), circucy related biomarkers, safety labs and vital
Scheduled Study Visit (Protocol	Analysis Visit Window (Study Day)
Scheduled Day)	
Baseline	≤1
Week 0 (Day 1)	1
Week 0 (Day 2) ^a	2
Week 2 (Day 15 ± 3)	2 to 22, or 3 to 22 ^a
Week 4 (Day 29 ± 3)	23 to 43
Week 8 (Day 57 ± 3)	44 to 71
Week 12 (Day 85 ± 7)	72 to 99
Week 16 (Day 113 ± 7)	100 to 141
Week 24 (Day 169 ± 7)	142 to 197
Week 32 (Day 225 \pm 7)	198 to 253
Week 40 (Day 281 ± 7)	254 to 309
Week 48 (Day 337 ± 7)	310 to 351
Week 52 (Day 365 ± 14)	> 351
	nposite endpoints that include an endoscopy component and/or
	Assessment, health-related quality of life, ECGs, OCT, and PFT
Scheduled Study Visit (Protocol	Analysis Visit Window (Study Day)
Scheduled Day)	
Baseline	≤1
Week 0 (Day 1)	1
Week 0 (Day 2) ^a	2
Week 12 (Day 85 ± 7) ^b	66 to 113 (66 to 141 for assessments impacted by COVID-19
	pandemic, or impacted by the war in Ukraine) ^c
Week 32 (Day 225 ± 7) [PFT only]	198 to 253 (198 to 281 for assessments impacted by COVID-19
	pandemic, or impacted by the war in Ukraine) ^c
	337 to 393 (337 to 421 for assessments impacted by COVID-19
Week 52 (Day 365 \pm 14) ^b	pandemic, or impacted by the war in Ukraine) ^c

a. Applicable only for participants who require extended monitoring on Day 2 for vital signs and ECGs.

For cardiac remonitoring upon treatment reinitiation after Day 2, as manifested by more than 1 timed measurement in vital signs or electrocardiogram (ECG) parameters on the same collection date of an unscheduled visit, measurements will be mapped to analysis visit of Cardiac Remonitoring 1, Cardiac Remonitoring 2, etc. in the respective analysis dataset. For analysis, each timed measurement will be programmatically assigned to the nearest hourly timepoint (eg, Predose, 1-hour Postdose) based on their relationship to the dosing time on the same day. If the dosing date/time on the same day is missing, the timepoint will remain missing. Once mapped, these timed measurements from cardiac remonitoring visits will not be considered for any other analysis visit.

b Applicable to all Week 12 and Week 52 efficacy endpoints based on any component of Mayo clinic score, such as clinical remission and symptomatic remission.

c Assessments impacted by the COVID 19 pandemic are reported in the Date of Visit eCRF. COVID-19, coronavirus disease 2019; ECG, electrocardiogram; eCRF, electronic case report form; MMS, modified Mayo Score; OCT, optical coherence tomography; PFT, pulmonary function test; RB, rectal bleeding; SF, stool frequency. Assessments impacted by the war in Ukraine are reported in the protocol deviation document.

Windowing will be applied prior to any missing data calculations. The last nonmissing measurement taken prior to Day 1 (including unscheduled assessments) will be labeled as "Baseline". In the case where the last nonmissing measurement and the date of first dose coincide and time is not collected, if the measurement was planned in the protocol to be done prior to the date of first dose, that measurement will be labeled as "Baseline", not "Week 0". Unless stated otherwise, data from all visits including scheduled, unscheduled, and ET visits will be eligible for allocation to an analysis visit. The 2-Week and 4-Week Follow-Up visits will not be included in the visit windows and will be summarized separately without any window applied.

If two or more measurements for an endpoint fall in a same analysis visit window, the measurement with the date closest to the protocol scheduled visit day will be used in the analysis. If 2 measurements in the same analysis visit window are equidistant from the protocol scheduled visit day, the earlier one will be used in the analysis. If multiple measurements are available on the same day, then the average of the measurements will be used in the analysis, except for laboratory and ECG data where the assessment at the earliest time of the same day will be used. If both central and local assessments of the same ECG or lab test are available on the same day, the central result will take precedence over the local result.

For the overlapping visit windows at Week 12 and Week 8/16, a hierarchical algorithm will be applied as follows: always map to the Week 12 study visit if the study day falls within the visit window of the Week 12 study visit, then assess the other records for the Week 8 or Week 16 study visit. The same algorithm will be used for Week 48 and Week 52, with Week 52 taking priority.

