3.4.2. HRQoL Endpoints

- Scores and change from baseline at Weeks 12, 32 (UC-PRO only), and 52 in the following:
 - Two Ulcerative Colitis Patient-Reported Outcomes (UC-PRO) modules. UC-PRO scoring is derived by calculating the average using at least 4 out of 7 daily scores, using the visit date to determine the days to be used. UC-PRO is available on the participants eDiary 14 days prior to and 14 days after the projected visit date. Participant should complete UC-PRO when it becomes available on the device for the visit, continuing until the visit occurs.
 - UC-PRO Signs and Symptoms (UC-PRO/SS). It is a 9-item questionnaire containing 2 domains: Bowel movement signs and symptoms (6 items) and functional symptoms (3 items). An average score is calculated for each domain; a higher score indicates worse symptoms.
 - UC-PRO Systemic Symptoms. The Systemic Symptoms measure includes 5 items, scored as a single scale, to address the presence and severity of systemic symptoms including pain, feeling tired, lack of appetite, feeling weak, and thirst.
 - Functional Assessment of Chronic Illness Therapy-Fatigue (FACIT-F). It is a 13-item fatigue instrument utilized to assess fatigue/ tiredness and its impact on daily activities and functioning in a number of chronic diseases. The instrument includes items such as tiredness, weakness, listlessness, lack of energy, and the impact of these feelings on daily functioning (eg, sleeping, and social activities).
 - Work Productivity and Activity Impairment Questionnaire Ulcerative Colitis (WPAI-UC). It consists of 6 questions asking about the effect of UC on the participant's ability to work and perform regular activities. The percent work time missed due to problem (absenteeism), percent impairment while working due to problem (presenteeism), percent overall work impairment due to problem, and percent activity impairment due to problem are derived on the eCRF directly. Details about derivation can be found in Section 9.2.1.
 - Urgency numeric rating scale (NRS). It is a single item that measures the severity for the urgency (sudden or immediate need) to have a bowel

- movement in the past 24 hours using an 11-point NRS ranging from 0 (no urgency) to 10 (worst possible urgency).
- Inflammatory Bowel Disease Questionnaire total score (IBDQ). It is a 32item self-administered questionnaire which has 4 dimensions: bowel
 symptoms (10 items), systemic symptoms (5 items), emotional health (12

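### SAP Table 9 reserves the Week 32 window for pulmonary function tests in the block that holds quality of life, so the planned Week 32 UC-PRO timepoint has no stated window

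*SAP*

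**What the plan says.** SAP 3.4.2 defines the quality-of-life endpoints as "Scores and change from baseline at Weeks 12, 32 (UC-PRO only), and 52". Protocol 10.10.2 names the same timepoints. The protocol's schedule of assessments marks the Week 32 questionnaire cell as applying to UC-PRO alone.

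On allocating data to visits, SAP 9.1.3 states that "efficacy, safety, HRQoL, and biomarker data (including scheduled, retests, unscheduled, and early termination) will be assigned to visits" using the windowing conventions of 9.1.4. Those conventions are in Table 9, which has two blocks:

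- The first block covers efficacy other than endoscopy, MMS and histology, together with efficacy-related biomarkers, safety laboratory tests and vital signs.
- The second block's heading includes "health-related quality of life, ECGs, OCT, and PFT". Its post-baseline rows from Week 12 onward are Week 12, Week 32 and Week 52, and the Week 32 row is labelled "Week 32 (Day 225 ± 7) [PFT only" (the bracket closes there).

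SAP 5.2.2 and Table 7 analyse quality-of-life endpoints with a linear mixed-effect model that reports treatment differences by visit.

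**The concern.** The endpoint section and the windowing table disagree. One plans a Week 32 UC-PRO result. The other puts quality of life in a block whose Week 32 row is expressly limited to a different assessment. A programmer who follows Table 9 has no rule that places a UC-PRO score taken near Day 225 in an analysis visit.

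Two things are at stake:

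- The planned Week 32 summaries and model estimates for the two UC-PRO modules (Signs and Symptoms, and Systemic Symptoms) would have no data.
- The repeated-measures model would have nothing from UC-PRO between Weeks 12 and 52. Estimand 2 (SAP 2.2.4) uses data collected up to the intercurrent event. A participant who stopped treatment after the Week 32 visit but before the Week 52 window opens would then contribute no UC-PRO information beyond Week 12, although a planned score exists.

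**Working it through.** No power or alpha figure is involved. The check is whether each scheduled Week 32 day falls inside a window that applies to UC-PRO.

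**Inputs** (all from SAP Table 9, second block)

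| Row | Standard window | If affected by COVID-19 or the war | Open to UC-PRO as labelled? |
|---|---|---|---|
| Week 12 | Days 66–113 | Days 66–141 | Yes |
| Week 32 | Days 198–253 | Days 198–281 | No (PFT only) |
| Week 52 | Days 337–393 | Days 337–421 | Yes |

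**Step 1: reproduce the plan's scheduled days.** Scheduled day = 7 × week + 1. Week 12: 7 × 12 + 1 = 85. Week 32: 7 × 32 + 1 = 225. Week 52: 7 × 52 + 1 = 365. All three match Table 9. With the ± 7 allowance, the Week 32 visit runs from Day 218 to Day 232, which is 232 − 218 + 1 = 15 days.

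**Step 2: map those days as the table is labelled.** Day 218 lies after the close of the Week 12 window (Day 113, or Day 141 if affected). Day 232 lies before the Week 52 window opens (Day 337). So 0 of 15 days map to any UC-PRO visit, in the standard and the extended version alike.

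**Step 3: map them with the Week 32 row opened to UC-PRO.** Days 218 to 232 lie inside 198–253 and inside 198–281, so 15 of 15 days map to Week 32.

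**Step 4: size the part due to the label.**

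- The whole stretch without a UC-PRO window is Days 114–336, which is 336 − 114 + 1 = 223 days. For affected assessments it is Days 142–336, which is 195 days.
- Opening the row recovers Days 198–253, which is 253 − 198 + 1 = 56 days. For affected assessments it recovers Days 198–281, which is 84 days.
- The remaining 223 − 56 = 167 days (114–197 and 254–336) stay unassigned after the repair, because no UC-PRO visit is planned there.

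The window attributable to the label is therefore 56 days. In timepoints, it is one of the three planned post-baseline UC-PRO assessments.

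**The case against.** The strongest reply is that the intent is plain. SAP 3.4.2 states the Week 32 UC-PRO endpoint outright, the protocol schedule collects it at Day 225 ± 7, and UC-PRO scoring already uses the visit date to choose which daily scores to average. A specific endpoint definition competes with a bracketed row label, and a careful programmer would raise a query before dropping the data. This stands as far as it goes. A reader might infer that the Week 32 results cannot be produced, or that the plan means to discard them. The documents do not support that: the endpoint is still planned, and 9.1.3 does not say that Table 9 is the only route to a visit. The scoring rule, however, selects diary days. It does not allocate a score to an analysis visit.

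A second reply is that the first block of Table 9 also gives Week 32 as Days 198–253, and that Protocol 9.8.4 describes these instruments as supporting the efficacy outcomes. The agreement of the standard window is a fair point, because it leaves no real analytic choice for unaffected assessments. But the SAP lists quality of life separately from efficacy (9.1.3 and 6.1), and Table 9 names it in the other block. The first block also has no extension for COVID-19 or the war: Days 254–281 fall in its Week 40 window (254–309), whereas the second block would keep affected assessments at Week 32. The two routes are therefore not fully equivalent.

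A third reply concerns scale, and it stands. UC-PRO is not in the nine-step test sequence of SAP 5.1, listings would still show the scores, and the documents give no count of participants who stop between Weeks 32 and 52. The effect on the Week 52 model estimate is therefore unknown. The 223-day gap would also overstate the defect, since most of it is unassigned by design.

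Part of the second block's heading is cut off in the text read, but the words on quality of life and the PFT restriction are both legible.

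**Conclusion.** The conflict is real and minor. Read literally, Table 9 gives UC-PRO no window at Week 32: 0 of 15 scheduled days are mapped, and one of three planned post-baseline timepoints is lost for both modules. The mixed model also loses its only planned UC-PRO observation between Weeks 12 and 52. The affected range is Days 198–253, or 198–281 for assessments affected by COVID-19 or the war.

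This loss assumes that the row label is programmed as written and that quality of life is windowed under the block that names it. If the programmer instead follows SAP 3.4.2, the data are kept, but by a decision that the SAP does not record.

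A reader might infer a wider effect on quality of life or on the trial's main conclusions. The documents do not support either. IBDQ, SF-36, FACIT-F, WPAI-UC, urgency NRS and PGIC have no planned Week 32 assessment. UC-PRO at Weeks 12 and 52 has working windows. The primary and key secondary analyses do not use UC-PRO.

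**What to change.** In the second block of SAP Table 9, relabel the Week 32 row as PFT and UC-PRO only. Keep Days 198 to 253, and Days 198 to 281 for assessments affected by COVID-19 or the war in Ukraine. Make the change before unblinding, so that the allocation of Week 32 UC-PRO scores is pre-specified.

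The cost is one label in the SAP and one line in the windowing program. The day ranges are already in the table, so no new analytic choice is introduced and nothing else in the plan has to change.
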